#### ANNEX 4. STUDY COVARIATES

N	Category	Variables	Definition
1	Demographic characteristics	Age	- By year (calculated on index date)
		Gender	- Male, Female
2	Ischemic and hematologic characteristics	CHA2DS2-VASc score	Codes used to define elements of CHA2DS2-VASc score in the following excel file:   11600308 CHA2DS2_VASc.xlsx
		HAS-BLED score	Codes used to define elements of HAS- BLED score in the following excel file:   1160-0308 HASBLED.xlsx
3	Comorbidities	Heart failure	ICD-10 diagnosis codes presented in the following excel file:
		Peripheral arterial disorder	
		Hypertension	
		Diabetes	

# BOEHRINGER INGELHEIM Group of Companies

## Statistical and Epidemiological Analysis Plan (SEAP) for Non-Interventional Studies (NIS)

c38948754-01

Page 24 of 32

Proprietary confidential information © 2022 Boehringer Ingelheim International GmbH or one or more of its affiliated companies

		Prior stroke/transient ischemic attack (TIA)/SE Cerebrovascular disease Myocardial infarction Acute Coronary Syndrome Unstable angina Bleeding history Renal dysfunction Hepatic dysfunction Cancers Peptic ulcer disease Obesity	 1160-0308 Comorbidities.xlsx
4	Co-medications	Anti-platelet drugs	Anti-platelet drugs include aspirin, clopidogrel, ticagrelor and prasugrel. The number of anti-platelet drugs is the number of anti-platelet drugs prescribed on the earliest prescription date before or on the index date during the look back period. Anti-platelet use duration is based on the number of days from the earliest anti-platelet prescription date to the index date.  Receipt codes presented in the following excel file:   1160-0308 Comedication.xlsx
		The number of anti-platelet drugs per prescription	
		Anti-platelet use duration	
		Nonsteroidal anti-inflammatory drugs	
		Gastric secretion inhibitors	
		Statins	
		Heparins	
		Proton pump inhibitor	
		Antihypertensive drugs	
5	Medical procedures	Cardioversion procedures	 Receipt codes presented in the following excel file:   1160-0308 Medical procedure.xlsx
		Ablation procedures	
		Percutaneous Coronary Intervention or Coronary Artery Bypass Grafting	

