##### **Primary outcome:**

- Fatal or non-fatal major bleeding (defined as any blood transfusion and/or any hospitalization with associated bleeding) in all three patient groups

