**Comorbidities (has at least 1 diagnosis before or on the index date during the look-back period)**

- Heart failure (yes/no)
- Peripheral arterial disorder (yes/no)
- Hypertension (yes/no)
- Diabetes (yes/no)
- Prior stroke/transient ischemic attack (TIA)/SE (yes/no)
- Cerebrovascular disease (yes/no)
- Myocardial infarction (yes/no)
- Acute Coronary Syndrome (yes/no)
- Unstable angina (yes/no)
- Bleeding history (yes/no)
- Renal dysfunction (yes/no)
- Hepatic dysfunction (yes/no)
- Cancers (yes/no)
- Peptic ulcer disease (yes/no)
- Obesity (yes/no)

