**9.4 DATA SOURCES**

The [REDACTED] database is one of the largest databases in Japan, collecting data from over 400 acute care hospitals which account for 25% of emergency hospitals in Japan. The database contains comprehensive medical record data,

blood test result data, insurance claims data, and pharmacy claims data, covering more than 35 million patients, 34% of whom are  $\geq$  65 years old. Each patient is assigned a specific identification number (ID) to which all inpatient and outpatient data are linked. The diagnosis is coded according to the 10th Revision of the International Classification of Diseases (ICD-10) codes or local disease codes.

The distribution of demographic characteristics, including age and sex, of patients registered in the [REDACTED] database is very similar to the distribution of these characteristics of patients visiting hospitals in Japan.

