### **8.2 OUTCOMES**

#### **8.2.1 Primary outcomes**

Operational definition of fatal or non-fatal major bleeding is the first new confirmed diagnosis of

- blood transfusion (inpatient or outpatient)  
OR
- bleeding of inpatient (non-DPC hospital)  
OR
- bleeding of inpatient (DPC hospital) with “disease name behind this hospitalization” (“dpcdiseasesegment”=21)

during the follow up period. The ICD-10 diagnosis codes of blood transfusion and bleeding are in [Annex 3](#).

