# BOEHRINGER INGELHEIM Group of Companies

## Statistical and Epidemiological Analysis Plan (SEAP) for Non-Interventional Studies (NIS)

c38948754-01

Page 22 of 32

Proprietary confidential information © 2022 Boehringer Ingelheim International GmbH or one or more of its affiliated companies

Blood transfusion	K92.0	Haematemesis
	D50	Iron deficiency anaemia
	D50.0	Iron deficiency anaemia secondary to blood loss (chronic)
	D50.1	Sideropenic dysphagia
	D50.8	Other iron deficiency anaemias
	D50.9	Iron deficiency anaemia, unspecified
	D62	Acute posthaemorrhagic anaemia
	D64.9	Anaemia, unspecified
	H35.6	Retinal haemorrhage
	I31.2	Haemopericardium, not elsewhere classified
	I60	Subarachnoid haemorrhage
	I60.0	Subarachnoid haemorrhage from carotid siphon and bifurcation
	I60.1	Subarachnoid haemorrhage from middle cerebral artery
	I60.2	Subarachnoid haemorrhage from anterior communicating artery
	I60.3	Subarachnoid haemorrhage from posterior communicating artery
	I60.4	Subarachnoid haemorrhage from basilar artery
	I60.5	Subarachnoid haemorrhage from vertebral artery
	I60.6	Subarachnoid haemorrhage from other intracranial arteries
	I60.7	Subarachnoid haemorrhage from intracranial artery, unspecified
	I60.8	Other subarachnoid haemorrhage
	I60.9	Subarachnoid haemorrhage, unspecified
Bleeding	I61	Intracerebral haemorrhage
	I61.0	Intracerebral haemorrhage in hemisphere, subcortical
	I61.1	Intracerebral haemorrhage in hemisphere, cortical
	I61.2	Intracerebral haemorrhage in hemisphere, unspecified
	I61.3	Intracerebral haemorrhage in brain stem
	I61.4	Intracerebral haemorrhage in cerebellum
	I61.5	Intracerebral haemorrhage, intraventricular
	I61.6	Intracerebral haemorrhage, multiple localized
	I61.8	Other intracerebral haemorrhage
	I61.9	Intracerebral haemorrhage, unspecified
	K92.2	Gastrointestinal haemorrhage, unspecified
	M25.0	Haemarthrosis
	M25.00	Haemarthrosis, multiple sites
	M25.01	Haemarthrosis, shoulder region
	M25.02	Haemarthrosis, upper arm
	M25.03	Haemarthrosis, forearm
	M25.04	Haemarthrosis, hand
	M25.05	Haemarthrosis, pelvic region and thigh
	M25.06	Haemarthrosis, lower leg

Proprietary confidential information © 2022 Boehringer Ingelheim International GmbH or one or more of its affiliated companies

	M25.07	Haemarthrosis, ankle and foot
	M25.08	Haemarthrosis, other
	M25.09	Haemarthrosis, site unspecified
	N92.0	Excessive and frequent menstruation with regular cycle
	R04	Haemorrhage from respiratory passages
	R04.0	Epistaxis

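### Baseline anaemia is not a named covariate, although anaemia codes are in the primary-outcome code list and the protocol counts any transfusion as major bleeding

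*SAP*

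**What the plan says.** **Outcome.** Protocol 9.3.2.1 defines the primary outcome as "Fatal or non-fatal major bleeding (defined as any blood transfusion and/or any hospitalization with associated bleeding) in all three patient groups". SAP 8.2.1 makes it operational as a first, new, confirmed diagnosis in one of three limbs. The first limb is "blood transfusion (inpatient or outpatient"); the other two are inpatient bleeding in non-DPC and in DPC hospitals. On identification, the SAP says "The ICD-10 diagnosis codes of blood transfusion and bleeding are in" Annex 3. That list includes D50 and its subcodes, D62 and D64.9; two of the descriptions (D50.9 and D64.9) contain "anaemia, unspecified". Protocol 9.3.2 adds that all outcomes must be incident after the index date.

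**Covariates.** SAP 11.1 builds the generalized propensity score (GPS) from the Annex 4 variables, less two antiplatelet variables that are redundant. The Annex 4 comorbidities end with "Bleeding history Renal dysfunction Hepatic dysfunction Cancers Peptic ulcer disease Obesity". Protocol 9.3.3 has the same comorbidities. Neither list names anaemia, haemoglobin or an earlier transfusion, and the Table 2a shells in both documents have no such row. No exclusion criterion removes patients with anaemia or a recent transfusion.

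**Laboratory data.** Protocol 9.4 says that the source holds "blood test result data, insurance claims data, and pharmacy claims data". SAP 7.1 agrees, and SAP 8.3 uses creatinine, liver enzymes and bilirubin for HAS-BLED. Protocol 9.9 says that laboratory results are not included.

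**The concern.** A patient who is already anaemic when the anticoagulant is started is close to the state that the outcome codes record. Anaemia is also visible to the prescriber, so it may influence the choice between warfarin and a NOAC. A variable that can affect treatment choice and is tied to the outcome definition belongs in the adjustment set.

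The plan has no second line of defence. The balance check covers only listed covariates. SAP 11.1 adds to the Cox model only covariates found out of balance, so a variable that is never tabulated cannot be picked up there. At stake is unmeasured bias in the primary hazard ratio for both NOAC comparisons, from a condition whose codes the analysis already uses.

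**Working it through.** The plan gives no figure on this point to reproduce: there is no anaemia prevalence and no anaemia–bleeding association. The check has two parts.

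**1. Can an anaemia code produce a primary event?**

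The Annex 3 table is broken in the available text, so the limb to which the anaemia codes belong is uncertain.
- If they belong to the transfusion limb, they count in inpatients and outpatients.
- If they belong to the bleeding limb, they count in inpatients only and, in DPC hospitals, only when flagged as the disease behind the hospitalization.

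On either reading an anaemia diagnosis can be a primary event. The new and incident wording restricts this, but no washout is defined. If re-coding of a chronic anaemia after index counts as new, anaemic patients have more such events. If a code already present in the look-back cannot count again, they may have fewer. So even the sign of the association is not fixed by the text.

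**2. How large could the bias be?**

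Take one yes/no confounder that does not modify the treatment effect. The hazard ratio is multiplied by

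B = [1 + pN(RR − 1)] / [1 + pW(RR − 1)]

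where pN and pW are the anaemia prevalences remaining after weighting in the NOAC and warfarin groups, and RR is the rate ratio for a primary event. All three are assumptions.

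| pW | pN | RR | B | B if prevalences are swapped |
|---|---|---|---|---|
| 20% | 18% | 1.5 | 1.09/1.10 = 0.99 | 1.01 |
| 20% | 18% | 2 | 1.18/1.20 = 0.98 | 1.02 |
| 20% | 15% | 2 | 1.15/1.20 = 0.96 | 1.04 |
| 30% | 15% | 4 | 1.45/1.90 = 0.76 | 1.31 |

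To put the 0.96 case on the plan's scale, ln(1.15/1.20) = −0.043. Protocol 9.5 plans on hazard ratios of 0.66 (ln = −0.416) and 0.74 (ln = −0.301), so the shift is about 10% and 14% of those effects. It would turn 0.66 into 0.63 and 0.74 into 0.71; reversed, into 0.69 and 0.77.

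For rivaroxaban vs warfarin, Protocol 9.5 expects 11,000 and 17,000 patients. At 3 events per 100 patient-years and 1 year each, that is 28,000 × 0.03 = 840 events. Ignoring weighting and sample loss, the 95% half-width on the log scale is 1.96/√(840 × 11/28 × 17/28) ≈ 0.14. The assumed shift of 0.043 is about a third of it.

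Would the plan's own rule catch such an imbalance? For 20% vs 15%, the absolute standardized difference (ASD) is 0.05/√[(0.20 × 0.80 + 0.15 × 0.85)/2] = 0.05/0.379 = 0.13. That is above the 0.1 limit, so it would be flagged and adjusted for if the row existed. For 20% vs 18% it is 0.05, which passes, and there B is only 0.98 at a rate ratio of 2.

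**The case against.** Several objections have force.

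- **Unseen code files.** The codes for bleeding history, the other comorbidities and HAS-BLED are in attachments that are not visible. The abbreviation list expands the HAS-BLED item to cover predisposition to bleeding, though SAP 8.3 uses only a bleeding-history diagnosis. Anaemia may therefore be inside an existing covariate, and a flat statement that it never enters the GPS is not supported. Even then it would be pooled with overt bleeding and have no balance row of its own.
- **Transfusion.** A reader might infer that any transfusion, with or without bleeding, is what the SAP counts. The protocol wording allows this. The SAP identifies the limb by ICD-10 diagnosis codes, and Annex 3 shows no transfusion procedure code. Whether a transfusion as such produces an event cannot be established.
- **Size and direction.** A reader might infer a large bias in favour of the NOACs, for example 1.30/1.50 = 0.87 from prevalences of 25% and 15% with a rate ratio of 3. Nothing in the documents supports these inputs or the direction. What matters is imbalance after weighting on age, HAS-BLED, bleeding history, renal dysfunction, cancer, peptic ulcer and co-medication, which would absorb part of any crude difference.
- **Available data.** A reader might infer that haemoglobin and earlier transfusions are ready to use. The documents conflict on laboratory data and show no transfusion code list.
- **Acknowledged limits.** Protocol 9.9 concedes residual confounding from absent data. It does not name anaemia, and the anaemia diagnosis codes are not absent.

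These points limit the size and certainty of the concern. They do not explain why a condition coded as part of the outcome has no baseline counterpart.

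**Conclusion.** The omission stands: anaemia codes can contribute to the primary outcome, and baseline anaemia is neither a named covariate nor checked for balance. Whether it reaches the GPS through the bleeding-history file cannot be determined. The new and incident wording protects only in part, because no washout is stated.

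The possible bias is of unknown size and sign. Under modest assumed residual imbalance the factor is about 0.96 or 1.04. Values such as 0.76 or 1.31 need prevalences of 30% and 15% to remain after weighting, together with a rate ratio of 4. All these figures assume a single yes/no confounder with no effect modification. The point is a gap in adjustment that is cheap to close; it does not show that the primary comparison is biased.

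**What to change.** Add one yes/no covariate to Protocol 9.3.3, SAP Annex 4, the GPS model and Table 2: an anaemia diagnosis in the look-back or on the index date, using the Annex 3 anaemia codes and kept separate from bleeding history. Apply the existing ASD rule, with Cox adjustment if it exceeds 0.1.

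Two additions are conditional:
- transfusion in the look-back, only if a transfusion code list can be specified;
- last pre-index haemoglobin, only if the conflict between Protocol 9.4, SAP 7.1 and SAP 8.3 on one side and Protocol 9.9 on the other is settled in favour of availability. The missing-data category in SAP 10.2 would then apply.

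The cost is small. In a three-group multinomial model, each yes/no covariate adds two coefficients (3 − 1), against about 4,000 patients expected in the smallest group. There is one more variable to derive and check, and no new data collection. Under SAP 10.2 the absence of a code is read as absence of the condition, so the anaemia covariate has no missing values.

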**Baseline co-medication (had used the drug before or on the index date during the look-back period)**

- Anti-platelet drugs (include aspirin, clopidogrel, ticagrelor, prasugrel) (yes/no)
- The number of anti-platelet drugs per prescription (single antiplatelet, dual antiplatelet, none)
- Antiplatelet use duration (single antiplatelet use: 6 months to 1 year, single antiplatelet use: 1 month to 6 months, single antiplatelet use: <1 month, dual antiplatelet use: 6 months to 1 year, dual antiplatelet use: 1 month to 6 months, dual antiplatelet use: <1 month, none; measured from the first antiplatelet prescription to baseline)
- Nonsteroidal anti-inflammatory drugs (yes/no)
- Gastric secretion inhibitors (yes/no)
- Statins (yes/no)
- Heparins (yes/no)
- Proton pump inhibitor (yes/no)
- Antihypertensive drugs (yes/no)

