### **8.3 COVARIATES**

Please check section 9.3.3. of the study protocol. List of covariates and operational definitions are added to [Annex 4](#).

The HAS-BLED score is calculated as the total points of the following elements (1 point per element) during the baseline period including the index date.

- Confirmed diagnosis of hypertension
- Dialysis-dependent kidney disease including confirmed diagnosis of hepatic dysfunction or confirmed diagnosis of renal dysfunction or on hemodialysis treatment
  - OR
- Confirmed diagnosis of cirrhosis
  - OR
- Renal transplant
  - OR
- Serum creatinine > 200 m mol/L
  - OR
- ALP > 3x upper limit (1050 IU/L) or ALT > 3x upper limit (132 IU/L) or AST > 3x upper limit (114 IU/L)
  - OR
- Bilirubin > 2x upper limit (2.4 mg/dL)
- Confirmed diagnosis of stroke
- Confirmed diagnosis of bleeding history
- Age calculated as of index date > 65 years old
- Confirmed diagnosis of excessive alcohol use
  - OR
- on treatment of excessive alcohol use
  - OR
- on antiplatelet drugs or non-steroidal anti-inflammatory drug

The CHA2DS2-VASc score is calculated as the total points of the following elements during the baseline period including the index date.

- Confirmed diagnosis of congestive heart failure (1 point)
- Hypertension (1 point) including confirmed diagnosis of hypertension or on any anti-hypertensive medications
- Age calculated as of index date  $\geq$  75 years old (2 points)

---

Proprietary confidential information © 2022 Boehringer Ingelheim International GmbH or one or more of its affiliated companies

- Diabetes Mellitus (1 point) including confirmed diagnosis of diabetes mellitus or on any anti-hyperglycemia agents or on any insulin treatment
- Confirmed diagnosis of stroke (2 points)
- Vascular disease including confirmed diagnoses of MI or peripheral arterial disorder (1 point)
- Age between 65 and 74 (1 point)
- Female (1 point)

The code used to define the elements of HAS-BLED score and CHA2DS2-VASc score are in [Annex 4](#).

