### **11.1 MAIN ANALYSIS**

During the first step of the comparative analysis, the baseline characteristics of the individual NOAC groups will be balanced with the warfarin group to account for potential confounding effects through an inverse probability of treatment weighting (IPTW) method. A multinomial logistic regression model will be used to estimate the generalized propensity score (GPS). The treatment membership (warfarin, dabigatran and rivaroxaban) is the dependent variable and all the covariate variables listed in [Annex 4](#) except for “Anti-platelet drugs” and “The number of anti-platelet drugs per prescription” are independent variables in the multinomial logistic regression model, as the two variables can be fully derived from the variable “Anti-platelet use duration”. For each patient, we will obtain the estimated GPS vector with components of the probabilities of receiving each treatment (warfarin, dabigatran and rivaroxaban) through the multinomial logistic regression model.

The stabilized IPTW (s-IPTW) will be used to deal with the inflation of type I error and extremely large weight when using regular IPTW. The s-IPTW is calculated as

$$w_i = \frac{\Pr(T = k)}{\Pr(T = k|X = x_i)}$$

for the  $i$ th patient, where  $T$  is the treatment membership and  $x_i$  is the covariates of this patient. The denominator is the  $k$ th component of GPS vector of the  $i$ th patient who was actually in treatment group  $k$  and the numerator is the marginal probability of receiving treatment  $k$  [\[R22-1420\]](#).

The GPS distributions (density curves, boxplots) of each treatment will be used to examine GPS overlap between the treatment groups. Patients outside of the common support or overlap area for any component of the GPS vector are removed from the analysis. The area of common support is formed by defining boundaries for each component  $k$ ,  $k = 1, 2, 3$  of the GPS vector [\[R22-1419\]](#):

$$\Pr(T = k|x)^{low} = \max[\min(\Pr(T = k|x, T = 1)), \min(\Pr(T = k|x, T = 2)), \min(\Pr(T = k|x, T = 3))]$$

$$\Pr(T = k|x)^{high} = \min[\max(\Pr(T = k|x, T = 1)), \max(\Pr(T = k|x, T = 2)), \max(\Pr(T = k|x, T = 3))]$$

[figure not shown]
The distributions of s-IPTW for each treatment group will be examined, the mean s-IPTW is expected to be close to 1. Weight truncation based on the distributions of s-IPTW will be applied if there are extremely high s-IPTW.

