# BOEHRINGER INGELHEIM Group of Companies

## Statistical and Epidemiological Analysis Plan (SEAP) for Non-Interventional Studies (NIS)

c38948754-01

Page 28 of 32

Proprietary confidential information © 2022 Boehringer Ingelheim International GmbH or one or more of its affiliated companies

Peptic ulcer disease; n (%)								
Cerebrovascular disease; n (%)								
Obesity; n (%)								
Anti-platelet drugs (include aspirin, clopidogrel, ticagrelor, prasugrel); n (%)								
The number of anti-platelet drugs per prescription (single antiplatelet, dual antiplatelet, none); n (%)								
single antiplatelet;								
dual antiplatelet;								
none;								
Antiplatelet use duration; n (%)								
Single Antiplatelet Use: 6 months to 1 year								
Single Antiplatelet								

**BOEHRINGER INGELHEIM Group of Companies****Statistical and Epidemiological Analysis Plan (SEAP) for Non-Interventional Studies (NIS)**

c38948754-01

Page 29 of 32

Proprietary confidential information © 2022 Boehringer Ingelheim International GmbH or one or more of its affiliated companies

Use: 1 month to 6 months								
Single Antiplatelet Use: <1 month								
Dual Antiplatelet Use: 6 months to 1 year								
Dual Antiplatelet Use: 1 month to 6 months								
Dual Antiplatelet Use: <1 month								
None								
Nonsteroidal anti-inflammatory drugs; n (%)								
Gastric secretion inhibitors; n (%)								
Statins; n (%)								
Heparins; n (%)								
Proton pump inhibitor; n (%)								
Antihypertensive drugs; n (%)								

Proprietary confidential information © 2022 Boehringer Ingelheim International GmbH or one or more of its affiliated companies

Cardioversio n procedures; n (%)								
Ablation procedures; n (%)								
Percutaneou s Coronary Intervention or Coronary Artery Bypass Grafting; n (%)								

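### Antiplatelet changes between the first look-back prescription and anticoagulant start are not captured in the propensity model

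*SAP*

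**What the plan says.** SAP Annex 4 (Co-medications) sets the count at one date: "The number of anti-platelet drugs is the number of anti-platelet drugs prescribed on the earliest prescription date" before or on index within the look-back. The second definition uses the same anchor: "Anti-platelet use duration is based on the number of days from the earliest anti-platelet prescription date to the index date". No stop date, gap or days of supply enters either definition.

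SAP 11.1 leaves the yes/no variable and the count out of the multinomial GPS model, "as the two variables can be fully derived from the variable" for duration of use. That is true: the duration variable has seven levels, single or dual crossed with under 1, 1-6 and 6-12 months, plus none. Table 2a in Annex 5 lists them, for example "Dual Antiplatelet Use: 6 months to 1 year".

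Protocol 9.3.3 treats co-medication as history: the patient "had used the drug before or on the index date during the look-back period". It anchors duration at the start, "measured from the first antiplatelet prescription to baseline". For the count it gives single, dual or none per prescription, and does not say which prescription decides.

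**The concern.** A patient on two drugs nine months before index who has since gone to one or none is coded the same as a patient still on two. A patient who started on one drug and had a second first prescribed on a later date stays coded as single. The regimen just before anticoagulant start, which bears on bleeding after it, is not itself a covariate.

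This covariate matters here because protocol section 7 names anticoagulant-antiplatelet co-prescription as what complicates AF with CAD, and the primary outcome is major bleeding. If changes of regimen before anticoagulant start differ between warfarin, dabigatran and rivaroxaban starters with the same coded history, the weighted comparison keeps some confounding. The absolute standardised difference (ASD) check and the fallback Cox adjustment in SAP 11.1 act only on listed covariates. Table 2a could therefore show antiplatelet use as balanced while the current regimen is not.

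**Working it through.** **Who is affected.** The documents give no figure to reproduce, so the first step is to follow the definitions through.

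- No antiplatelet prescription up to and including index: coded none, which is exact.
- First prescription on the index date: coded with the regimen of that day, which is exact, reading Annex 4 as including the index date.
- First prescription under 1 month before index: probably close, since there is little time for change.
- First prescription 1-6 or 6-12 months before index: any later change is lost. The gap lies mainly here.

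**What adjusts indirectly.** ACS, MI, unstable angina, PCI/CABG, bleeding history, peptic ulcer disease and proton pump inhibitor use are in the GPS as undated yes/no flags. HAS-BLED adds one point for drugs, but it is shared with NSAIDs and alcohol, covers the whole baseline period and does not separate single from dual.

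**Illustration of size.** Only the arm sizes come from the documents (protocol 9.5: 4,000 dabigatran, 11,000 rivaroxaban, 17,000 warfarin). Everything else is assumed, and the true ratio is set to 1.0.

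| Level | Dabigatran % | Rivaroxaban % | Warfarin % | Pooled % |
|---|---|---|---|---|
| Single <1 month | 8 | 9 | 10 | 9.41 |
| Single 1-6 months | 8 | 9 | 12 | 10.47 |
| Single 6-12 months | 24 | 22 | 18 | 20.13 |
| Dual <1 month | 5 | 7 | 12 | 9.41 |
| Dual 1-6 months | 5 | 7 | 12 | 9.41 |
| Dual 6-12 months | 10 | 11 | 11 | 10.88 |
| None | 40 | 35 | 25 | 30.31 |

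Base changes by index, for bands <1 / 1-6 / 6-12 months: dual to single 2/15/35%, dual to none 0/5/10%, single to dual 2/8/10%, single to none 0/5/10%. About 12-13% of patients change. Bleeding ratios for single (s) and dual (d) against none, by status at index, are 1.4/2.0 or 1.5/2.5.

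The stabilised weight Pr(T=k)/Pr(T=k|level) gives every arm the pooled distribution, so both NOAC comparisons yield the same ratio. Mean relative risk in weighted warfarin is M = 1.4170 (1.4/2.0) or 1.5856 (1.5/2.5).

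NOAC-minus-warfarin differences apply only in bands of 1 month or more. The pooled shares there are P_S = 0.1047 + 0.2013 = 0.3059 for single (unrounded sum) and P_D = 0.0941 + 0.1088 = 0.2028 for dual. With U, D and S the differences in single-to-dual, dual-to-single and single-to-none:

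ratio = 1 + [U(d−s)P_S − D(d−s)P_D − S(s−1)P_S] / M

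| D, U (points) | S=0: 1.4/2.0 | S=0: 1.5/2.5 | S=D: 1.4/2.0 | S=D: 1.5/2.5 |
|---|---|---|---|---|
| 0, 0 | 1.000 | 1.000 | 1.000 | 1.000 |
| +10, 0 | 0.991 | 0.987 | 0.983 | 0.978 |
| +10, −5 | 0.985 | 0.978 | 0.976 | 0.968 |
| +20, −8 | 0.972 | 0.959 | 0.955 | 0.940 |
| −10, 0 | 1.009 | 1.013 | 1.016 | 1.021 |
| −10, +5 | 1.015 | 1.022 | 1.022 | 1.030 |
| −15, +8 | 1.023 | 1.035 | 1.030 | 1.043 |

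For negative S the single-to-none rate is floored at zero, so S·P_S becomes −(0.05×0.1047 + 0.10×0.2013) = −0.0254.

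The extremes, for 1.5/2.5:

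- 1 − (0.08×0.3059 + 0.20×0.2028)/1.5856 = 1 − 0.0650/1.5856 = 0.959
- with stopping: 1 − (0.0650 + 0.20×0.5×0.3059)/1.5856 = 0.940
- opposite direction: 1 + (0.0245 + 0.15×0.2028)/1.5856 = 1.035
- with stopping: 1 + (0.0549 + 0.5×0.0254)/1.5856 = 1.043

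With equal change rates the crude ratios are 0.88-0.91 (dabigatran) and 0.92-0.94 (rivaroxaban), and the planned variable brings both to 1.000.

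**Sampling error for scale.** Assume 3 per 100 patient-years on warfarin, one year of follow-up and the protocol's hazard ratios. Events are 17,000×0.03 = 510 on warfarin, 4,000×0.03×0.66 = 79.2 on dabigatran and 11,000×0.03×0.74 = 244.2 on rivaroxaban. The unweighted 95% CI factors are exp(1.96√(1/79.2+1/510)) = 1.27 and exp(1.96√(1/244.2+1/510)) = 1.16.

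**The case against.** The strongest reply is that nothing has gone wrong. The protocol defines co-medication as history and anchors duration at the first prescription; the SAP implements that and fills in one thing left open. This stands: the SAP does not contradict the protocol.

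Next, most patients are coded correctly. About 87-88% are unchanged under the assumed rates, several covariates related to step-down are in the GPS, and any bias depends on a difference by arm that no document figure supports. This also stands, and it is why the point is minor.

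Third, current antiplatelet status may be part of the anticoagulant decision. If a drug is dropped on the day the anticoagulant starts, balancing on it could adjust away part of the treatment strategy. This stands against using index-date prescriptions in the main model. It has much less force for prescriptions written before index.

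Last, protocol 9.7.2 and SAP 11.2 are redacted, and the attached code files and full table shells are not visible, so a further antiplatelet analysis may exist. It would not change the main GPS as shown.

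Two stronger readings are tempting. A reader might infer that antiplatelet therapy goes unadjusted. It does not: number and time since first prescription are both in the GPS. A reader might also infer a large bias in favour of the NOACs. Within one coded level, assumed dual-use shares of 10% against 40% and a dual-to-single bleeding ratio of 2.0 give 1.1/1.4 = 0.79. That is one level with a large assumed gap, not an estimate for the study, and the documents fix neither size nor direction.

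**Conclusion.** The point holds in a limited form. Regimen change between first antiplatelet prescription and anticoagulant start is missing from the main GPS and invisible to its diagnostics, mainly in the two longer bands. It matters for the major-bleeding hazard ratio only if such change differs by arm within levels after the other covariates; if it does not, there is no bias from this source.

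The illustrated ranges rest on assumed inputs and on this covariate alone; the other covariates may shrink them. They are smaller than the sampling error at one year of follow-up. Unlike sampling error, however, this bias would not be reflected in the confidence interval. It is a cheap improvement worth making, not a defect that undermines the analysis.

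**What to change.** In Annex 4, add most-recent antiplatelet status before index: none, single, dual, or past use only. Derive it from the latest prescription(s) in the look-back before the index date, with a grace period stated in advance and a rule for combining drugs prescribed on different dates. Put it in the GPS and in Table 2a. Keep the earliest-date duration as a history variable, and collapse sparse or redundant cells (the two none levels largely coincide). State explicitly whether index-date prescriptions count in each variable. Repeat the analysis with them counted as a sensitivity analysis.

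The cost is a little programming on prescription records already used for Annex 4; no new data are needed. There are four downsides:

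- The new factor overlaps the duration variable.
- It may slightly increase trimming, because "Patients outside of the common support or overlap area for any component of the GPS vector are removed from the analysis".
- Refills obtained outside the database hospitals would be coded as past use (protocol 9.9 notes that the system is not closed).
- Days of supply is stated for exposure records (protocol 9.3.1) and should be confirmed for co-medications. If it is absent, the latest prescription date serves.
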